5. STUDY PROCEDURES

5.1 Provide a complete overview of the study:

- **Describe the procedures participants will be asked to complete or undergo.**
- **Explain step by step what participants will be asked to do**
- **Include how long the procedures will take.**

If your study includes multiple variations of the procedures, please make clear which procedures are included in the variations.

Recruitment. Recruitment materials will be distributed via a mass email to all enrolled students from the Dean of Students Office (DSO), announcements over house emails lists (e.g., academic departments), and social media announcements.

Pre-trial needs assessment and pilot. Prior to the full RCT, we will conduct a campus-wide needs assessment survey to gather information about student needs and preferences related to mental health programming. Student responses will inform the specifics of StriveWeekly implementation during the academic year (e.g., preferred timing of programming, appropriateness of content across a diverse student population). After the needs assessment, we will invite a small group of students to participate in a small pilot of the revised StriveWeekly platform. Students who participate in the pilot will be invited to provide their program feedback via online surveys. Students who participate in the pilot data collection will still be eligible for the full RCT study, but may be excluded from the final data analysis sample.

Pragmatic trial design. For an RCT of a self-guided online intervention, it is important that the design mimics intended intervention use (Fleming et al., 2018). As examples, overly stringent inclusion criteria limit generalizability, or face-to-face assessments may provide added benefit beyond the intervention itself (Fleming et al., 2018). Therefore, as much as possible our methods simulate how a real-world campus might offer online services as usual. First, we are employing cluster randomization, for reasons elaborated below. Second, participants in either condition will be allowed to access other on- or off-campus mental health services and resources; in our statistical analyses we will control for service use rather than excluding such students. Third, all data collection and participant communications will be electronic rather than in-person to: (a) include all students remote or on-campus, (b) avoid unintentionally bolstering motivation (e.g., inducing social desirability to please researchers), and (c) avoid adding barriers (e.g., time demands, concerns about privacy). Finally, survey compensation

amount will be modest enough to increase participant response rates without artificially inflating adherence rates or self-reported improvement due to financial incentive.

Random assignment. Cluster randomization will be used to assign students according to their residential affiliation to the **immediate intervention condition** or the **waitlist condition** (i.e., delayed access). This randomization plan has been discussed with the Dean of Students Office and was preferred over a fully randomized assignment of students. Although cluster randomization can introduce statistical confounds for analyzing intervention outcomes at the individual participant level, they can be preferred: (a) to avoid intervention “contamination” effects (e.g., if participants in both conditions can regularly interact and thus might exchange health-related knowledge), and (b) if it allows the intervention to be delivered as it would be in real practice (Cook, Delong, Murray, Vollmer, & Heagerty, 2016). Moreover, the benefits of cluster randomization by residential house/dorm affiliation for this trial are crucial for the social aspects of the StriveWeekly program. For example, students will know who else is concurrently participating in the program (e.g., any of their friends in X, Y, Z house), allowing for peer-to-peer engagement. Also, this will allow for easier coordination of any optional complementary programming by residential staff at each house/dorm. A randomizer was already used to assign half the freshmen and upperclassman residential buildings to each condition:

Immediate StriveWeekly Access	Delayed StriveWeekly Access
Houses: Adams, Cabot, Currier, Dudley, Mather, Quincy, Winthrop	Houses: Dunster, Eliot, Kirkland, Leverett, Lowell, Pforzheimer
Freshmen: Ivy Yard, Elm Yard	Freshmen: Crimson Yard, Oak Yard, Maple Yard

Data collection. Prior to beginning any research procedures, students will provide their informed consent online via Qualtrics. Participants will be required to login to Qualtrics via HarvardKey Shibboleth, which will be configured to only allow currently active Harvard accounts. Once consent has been obtained for an individual student, they will be directed to an online survey for the study **baseline assessment**. The baseline survey will be open for two weeks. Students assigned to the intervention group will receive an access code in the email, allowing them to access the online platform and set-up their account. The intervention group will then be active for seven weeks, after which the **posttest survey** will open to the intervention group and waitlist group for one-two weeks. There will then be a pause in study activity and data collection from mid-November through winter break. Thereafter, there will be a **2-month follow-up survey** and students who were assigned to the waitlist group will gain access to the online intervention for seven weeks. After this delayed access group completes the intervention, there will be a **5-month follow-up survey** for all participants from both conditions. After the fourth survey, subsets of participants may be invited to additional compensated opportunities to provide further feedback as research data. See timeline table below.

Activity	Timeline
Promotion	August 16 – Sept 6
Recruitment + Baseline Survey	Sept 7 – Sept 17
First Intervention Round	Sept 20 – Nov 7
•Weekly goal-setting & Time management	Sept 20 - 26
•Unhelpful thinking habits	Sept 27 - Oct 3
•Quality time on values & fun	Oct 4 - Oct 10
•Relaxation strategies & Mindfulness	Oct 11 - Oct 17
•Sleep hygiene	Oct 18 - Oct 24
•Physical exercise	Oct 25 - Oct 31

•Wrap-up	Nov 1 - Nov 7
Posttest Survey	Nov 8 – Nov 19
Break	
2-month Follow-up Survey	Jan 24 - Feb 4
Second Intervention Round	Feb 7 – Apr 3
•Weekly goal-setting & Time management	Feb 7 - Feb 13
•Unhelpful thinking habits	Feb 14 - Feb 20
•Quality time on values & fun	Feb 21 - Feb 27
•Relaxation strategies & Mindfulness	Feb 28 - Mar 6
•Sleep hygiene	Mar 7 - Mar 13
Spring break	Mar 14 – Mar 20
•Physical exercise	Mar 21 - Mar 27
•Wrap-up	Mar 28 - Apr 3
5-month Follow-up Survey	Apr 4 - 15
Additional feedback from subgroups TBD	April - May 2022

Conditions

Intervention group. When participants first access the platform (app.striveweekly.com) they are self-guided through an account set-up process. Then they customize their settings for timing and frequency of weekly reminder emails. Finally, the user engages in goal-setting, which includes selection of a program goals (e.g., mood management, anxiety reduction) and motivational enhancement strategies (e.g., writing reasons that this goal was important to them). The intervention program is then seven weeks long, including an introduction week module, five skills modules, and a maintenance planning module. Details of module contents are presented in below:

Module	Strategies/Skills	Example activities
1. Getting Set Up	Rationale and expectations	Watch the welcome video
	Self-monitoring prep	Check out the “Progress” dashboard
	Time management	Set SMART goals
2. Reframe	Cognitive monitoring	Identify any unhelpful thinking habits
	Cognitive distortions	Identify evidence for and against thoughts
	Cognitive restructuring	Shift your attention
3. Engage	Behavioral activation	Spend time on a hobby
	Activity scheduling	1. Clean and organize 2. Good deeds
4. Pause	Mindfulness	1. Deep breathing
	Relaxation	1. Progressive muscle relaxation 2. Meditate mindfully
5. Recharge	Sleep hygiene	1. Do relaxing activities pre-sleep 2. Make a worry list and set it aside
6. Move	Physical exercise	1. Try a new sport, fitness activity, or class
	Sleep hygiene	1. Spend time outdoors 2. Walk instead of ride
7. Looking Ahead	Maintenance planning	1. Review progress 2. Print out copies of favorite materials

Plan for triggers

Every Monday participants receive an email directing them to the instructions section of the online platform. Each module presents a checklist of activities for participants to complete as well as tips and suggestions for how to practice each module's skill. At the beginning of the week, participants make a "plan" indicating which activities/skills they intended to try and any barriers they expected to encounter. Throughout the week, participants can visit their user dashboard to log skills practice for the current module (within a seven-day grace period) along with ratings of their mood and stress levels, which are plotted in their self-monitoring graph. NOTE: Students do not complete any of the activities within the app (e.g., users do not record their unhelpful thinking habits during week 3), but rather they submit a log after practicing a skill outside of the app. At the end of each module participants are prompted to complete weekly check-in questions about their personal goal progress. Weekly prize drawings (items of \$10-40 value) will be offered to all participants submitting a weekly check-in. Students who had log activity for all modules will be eligible for the completer prize drawing (items of \$100-200 value).

There is also a "Campus" section of their dashboard that provides students with: info about relevant campus resources; a notification center with campus-specific messages and updates; and an anonymous livestream of all campus users' activity, to provide a sense of community. See screenshots of the online platform in the **Supplemental Materials** uploaded.

Finally, residential staff will be encouraged to offer complimentary programming (e.g., relevant themed study breaks), if they are so interested in doing so. These events will not involve any data collection, but the PI will contact residential staff (through approved coordination with the Dean of Students office) to document which houses/dorms held additional events, so that such information can be treated as a covariate in data analyses.

Waitlist group. Participants in this group will receive no intervention or communications between their baseline randomization and the invitation for posttest survey. They will be provided access to the online program after completing the posttest survey.

The below sections contain additional questions depending on the type of research that you are conducting and is meant to supplement the study overview. Please complete each section, as applicable.

SURVEYS/ QUESTIONNAIRES/PSYCHOMETRIC TESTING

Skip this section if not applicable.

5.2 List the names of all surveys/questionnaires/psychometric tests to be used in this study and a description of any that are not standard/formally named (such as study-specific questionnaires).

See full details in uploaded measure battery.

1. **Self-report demographic questionnaire** (age, gender, ethnicity, academic year).
2. **Branding feedback.** There will be a few questions about if students would have been more or less likely to sign-up for the program had it been under a different name (e.g. "The Happiness Challenge")
3. **Treatment Motivation Questionnaire (TMQ).** Questions from the Treatment Motivation Questionnaire (Ryan, Plant, & O'Malley, 1995) have been minimally adapted to apply to an online mental health promotion program instead of a treatment. Questions from the help-

seeking subscale were removed. This 20-question measure will assess participants' reasons for signing up and expectations for completing the program. The TMQ has significant predicted intervention completion in other research studies, for example in-person alcohol treatment (Ryan et al., 1995) and online trauma treatment (Alfonsson et al., 2016).

4. **Depression Anxiety and Stress Scale.** The primary symptom outcome measure will be the 21-item version of the Depression Anxiety and Stress Scale (DASS-21), which assesses self-reported symptoms related to depression, anxiety, and stress. The DASS-21 has demonstrated high internal consistency (.83 - .90) and good construct validity in university student samples (Norton, 2007). Note: There are no questions related to suicidality.
5. **Perceived Stress Scale.** This measure is a 10-item scale that is the most widely used psychological instrument for measuring the perception of stress. It is a measure of the degree to which situations in one's life are appraised as stressful. Items were designed to tap how unpredictable, uncontrollable, and overloaded respondents find their lives.
6. **Self-reported service use.** Students will be asked to indicate past and current use of health-related services on- and off-campus using a checklist of common resources/services (e.g., off-campus therapy, psychiatry at HUHS, etc.) as well as a write-in "other" option.
7. **Technology use.** Students will be asked to indicate the types of devices they use, their internet access, health data settings, etc.
8. **Checklists / weekly hour estimates of extracurriculars and regular behaviors.** See uploaded battery.
9. **Life Events Checklist.** Items combined from the following standardized measures: Life Events Scale for Children, Adolescent Perceived Events Scale, and Life Events Checklist for DSM-5 (LEC-5). Some original items added, including COVID-19-related items.
10. **General Belongingness Scale.** A standardized 12-item measure to assess a sense of general belongingness, which has been previously validated in student samples.

Pilot / Posttest / Follow-Up Survey Only

11. **Program satisfaction.** The posttest and follow-up surveys will include questions about experiences with the program for the respective group that just completed the intervention. This 5-item measure is adapted from the Client Satisfaction Questionnaire (Larsen, Attkisson, Hargreaves, & Nguyen, 1979), which has been found to be an appropriate measure of satisfaction with high internal consistency and concurrent validity across a broad range of intervention contexts (e.g., children's outpatient mental health services, Copeland, Koeske, & Greeno, 2004; adult outpatient setting, De Wilde & Hendriks, 2005; adult residential treatment setting, Kelly et al., 2018).
12. **Module preferences.** Students will be asked to rank the modules in order of the most to least favorite.
13. **Open-ended feedback.** There will be an open text field for participants to write any feedback they had about their experience.
14. **Tech-based intervention barrier scale.** A 10-item self-report scale to assess barriers experienced by users of tech-based interventions (Ramos, Hammons, Chavira, & Rith-Najarian, 2019)

Follow-Up Interview

15. **Study-specific semi-structured interview.** A subsample of students will be asked a series of open-ended questions to gather feedback about their experience with StriveWeekly and invite proposed adaptions to improve acceptability, feasibility, and engagement for a targeted sample of students endorsing identification with the LGBTQ+ community.

5.3 How often will participants be asked to complete the surveys/questionnaires/psychometric tests and how long will it take to complete?

- Baseline survey (approximately 10 minutes)
- Posttest survey (approximately 3-5 minutes)
- follow-up survey (approximately 3-5 minutes)

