Study title: Randomized Controlled Trial (RCT) of StriveWeekly for Anxiety and Depression Prevention for College Students During COVID-19

NCT #:NCT04927845

Document date: 06/01/2023

The following “Data analysis” section is an excerpt from a proposal titled “Randomized Controlled Trial of StriveWeekly during COVID-19” that was submitted on 08/14/2020 to Harvard University Foundations of Human Behavior Initiative Proposal.

Data analysis. For assessing intervention effects, piecewise LME models will be run in predicting change in outcome scores. Included variables of group, time, group by time interaction, and covariates will be treated as fixed effects, whereas participant intercepts and outcome slopes will be allowed to vary randomly. Between-group and with-group effect sizes (d) will be calculated based on estimated marginal means. Moderator and mediator analyses will be selected *post hoc*, based on data completeness. Given the number of exploratory analyses that will be conducted, all significant findings will be tested against Benjamini-Hochberg critical values, on order to control for false discovery rate (i.e., Type I error).

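### House and dorm events held after allocation may enter the primary model as a covariate, which could take part of the program's effect, and some precision, out of a posttest d (minor)

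*Protocol*

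**What the plan says.** Under the intervention group in Protocol 5.1, "residential staff will be encouraged to offer complimentary programming (e.g., relevant themed study breaks), if they are so interested in doing so". The investigator will contact those staff "to document which houses/dorms held additional events, so that such information can be treated as a covariate in data analyses". The protocol does not say which analysis, how the variable is coded, or whether event dates are kept.

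On the waitlist group the same section says: "Participants in this group will receive no intervention or communications between their baseline randomization and the invitation for posttest survey". It does not mention staff events in waitlist houses. The timeline in 5.1 gives those houses the same program in spring.

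The random-assignment text in 5.1 states that "the benefits of cluster randomization by residential house/dorm affiliation for this trial are crucial for the social aspects of the StriveWeekly program", and adds that "this will allow for easier coordination of any optional complementary programming by residential staff at each house/dorm". The buildings had already been allocated when this was written. The pragmatic-design text says that "as much as possible our methods simulate how a real-world campus might offer online services as usual".

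The SAP says: "Included variables of group, time, group by time interaction, and covariates will be treated as fixed effects". It adds that between-group and within-group "effect sizes (d) will be calculated based on estimated marginal means". It lists no covariates, does not limit them to baseline values, and does not say whether the between-group d is the posttest difference or the difference in change.

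**The concern.** A house event is something that happens after allocation and that allocation makes more likely. If the trial estimates the effect of the program as a campus would offer it, which the pragmatic-design and random-assignment text in 5.1 supports, events are one route by which the program works. Holding them constant removes that route from the estimate.

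The other possible target is the app alone, and Protocol 4.1 can be read that way. Adjustment does not deliver this cleanly either. Staff choose whether to hold events, so houses with and without them may differ in other ways, and the adjusted contrast is no longer the one that randomization protects.

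Two things are at stake: the size of a posttest d taken from marginal means, and its precision. Precision can suffer even if events do nothing, because the event indicator is correlated with arm.

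**Working it through.** The documents give no sample size, event frequency or event effect, so there is no planned figure to reproduce. The check shows how the adjustment acts and gives an illustrative size.

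**Inputs from the documents.** Clusters (5.1, random assignment): 7 houses + 2 yards = 9 immediate; 6 houses + 3 yards = 9 delayed. Illustrative total effect D = 0.25, the prior trial's result (4.2), counted as benefit.

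**Assumed.** Events in k = 5 of 9 immediate and 0 of 9 waitlist clusters; event effect e = 0.10 SD, absent at baseline; within-person correlation r = 0.6; 39 enrolled per cluster; retention of 70, 65 and 60% at the three later surveys; intracluster correlation 0.02.

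**Coding.** The only interaction the SAP lists is group by time, and the protocol describes a list of houses without dates. A time-constant main effect is therefore the closest reading.

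**Step 1: time-constant term, complete data.** The fitted event coefficient averages the event effect over surveys. If the effect is present in s of S surveys:

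posttest d = D − (k/9) × e × (s/S)

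- Two surveys: 0.25 − (5/9)(0.10)(1/2) = 0.222.
- Four surveys, effect persisting: 0.25 − (5/9)(0.10)(3/4) = 0.208.
- Group by time: the constant term cancels between baseline and posttest, so it stays 0.250 with an unchanged standard error. A difference-in-change d is likewise unchanged.

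**Step 2: precision, two surveys, complete data, no cluster variance.** The posttest value is the person mean plus half the change, with variance shares (1+r)/2 = 0.8 and (1−r)/2 = 0.2. Only the mean part is inflated, by (1/4 + 1/9)/(2/9) = 1.625. The SE factor is √(0.8 × 1.625 + 0.2) = √1.5 = 1.22.

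**Step 3: add dropout and clustering.** Generalized least squares with the assumptions above; ranges are over cluster-time correlations of 0, 0.5 and 1.

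| Event term | Posttest d | Group by time | SE factor for posttest d |
|---|---|---|---|
| Omitted | 0.250 | 0.250 | 1.00 |
| Constant, two surveys | 0.225–0.229 | 0.250 | 1.18–1.22 |
| Constant, four surveys, no waitlist events | 0.213–0.219 | 0.250 | 1.14–1.21 |
| Constant, four surveys, undated, 3 of 9 waitlist houses with spring events | 0.240–0.242 | 0.250 | 1.01–1.02 |
| Constant, four surveys, undated, 5 of 9 waitlist houses with spring events | 0.250 | 0.250 | 1.00 |

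With participant random terms only, as the SAP lists them, the two-survey d is 0.230–0.231.

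**Step 4: other codings.** A dated time-varying or event-by-time term gives 0.25 − (5/9)(0.10) = 0.194 for both posttest d and group by time.

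**Step 5: scale and sensitivity.** The unadjusted posttest d has a standard error of about 0.108 here. The two-survey shift of 0.021–0.025 is about 0.2 of that; the four-survey shift of 0.031–0.037 is about 0.3. Event effects of 0.05 and 0.15 SD give two-survey d values of about 0.24 and 0.21–0.22. With no event effect d stays 0.250, but the SE factor is about 1.1 with events in 3 of 9 immediate clusters and about 1.4–1.5 with 7 of 9. If all 9 immediate and no waitlist clusters hold events, the two effects cannot be separated.

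**The case against.** The strongest reply is that the main test does not move. Protocol 4.1 frames the hypothesis as change from baseline to posttest, and the SAP models change in outcome scores. Under the closest coding, group by time is untouched, and so is a d defined as the difference in change. This stands, and it limits the point to a posttest d, which the SAP neither adopts nor rules out.

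Second, the protocol only permits the adjustment and does not name the primary model. Exploratory use would fit the same words. This also stands.

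Third, waitlist houses get the program in spring, so an undated record covering both rounds could show similar event rates in both arms, and the shift would then largely disappear. This stands too: the four-survey result with no waitlist events is a corner case. If events were commoner in waitlist houses and helpful, adjustment could even raise d.

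Fourth, events might be regarded as an optional co-intervention to be removed, given the focus of 4.1 on the online intervention. That is a defensible target, but adjusting for events that staff choose to hold does not reach it cleanly.

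A reader might infer that the plan commits to adjusting for events and will therefore understate the effect or bias the main test. The documents support neither. The wording is permissive, the usual coding leaves group by time alone, and a lower group-by-time estimate needs a time-varying or event-by-time term that neither document proposes.

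**Conclusion.** The concern holds as a minor one. The protocol offers a variable that arises after allocation and is linked to arm as a possible covariate, and nothing in the SAP keeps it out of the primary model. If it is used there, a posttest d from marginal means could fall from 0.25 to about 0.23 with two surveys, with a standard error about 1.2 times as large.

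That size requires d to be the posttest difference, events to help, and events to be commoner in immediate-access houses. The last is an inference from the intervention and waitlist descriptions. Event counts, event effect, enrollment, retention and correlations are all assumed. Without an event effect there is no shift in d, only possible loss of precision.

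**What to change.** In the SAP:

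- Name the primary-model covariates and limit them to values from before program access.
- Keep house and dorm events out of the primary model.
- Report events by arm with dates, so that fall events and spring waitlist events are not mixed, or use them only in an analysis labelled exploratory.
- State whether the between-group d is the posttest difference or the difference in change.

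This takes one or two sentences and loses no data. The downside is that the primary estimate does not separate the app from house programming; that question moves to exploratory work.
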